7.9.1 Progesterone

Progesterone will be quantified by radioimmunoassay (RIA) following its extraction with ethyl acetate:hexane (2:3) and Celite column partition chromatography [136]. Approximately 1000 d.p.m. of ³H-progesterone will first be added to each serum sample to follow procedural loss. The RIA of purified progesterone will use iodinated progesterone in conjunction with a specific antiserum against progesterone. After an appropriate incubation period, a second antibody is used to separate antibody-bound progesterone from unbound progesterone. The resulting progesterone values will be corrected for procedural loss. Sensitivity of the assay is 0.2 ng/ml; intraassay and interassay coefficients of variation (CVs) are 8% and 9%, respectively.

7.9.2 Estradiol

Estradiol will be measured by RIA following extraction and Celite column partition chromatography [137]. The extraction step will utilize ethyl acetate:hexane (2:3). Following evaporation of the organic solvents, the extract will be applied on a column of Celite impregnated with ethylene glycol. Estradiol will be separated by elution with 15% ethyl acetate in isooctane and 40% ethyl acetate in isooctane, respectively. After evaporating the eluates, the residues will be redissolved in assay buffer, and appropriate aliquots will be taken for RIA. Each RIA uses a highly specific antiserum in conjunction with an iodinated radioligand. Following an appropriate incubation period, antibody-bound and unbound estradiol is separated using a second antibody. The antibody-bound fraction is then counted after centrifugation. Sensitivity of the estradiol assay is 5 pg/ml; intraassay and interassay CVs are 9.3% and 11.4%, respectively.

7.10 Breast MRI

While the majority of studies showing an association between breast density and breast cancer risk are based on mammographic measurements, mammography is generally not recommended for young women because of its reduced effectiveness of cancer detection in dense breast tissue, and the radiation exposure, which is quite low but cumulative. In this study of young women, we propose to use MRI to measure breast density. MRI is not impaired by high parenchymal breast density, making it especially effective for younger women with dense breast tissue. MRI can easily distinguish fibroglandular and fatty breast tissue and gives three-dimensional information not provided by mammography. Additionally, MRI does not use ionizing radiation. In studies using MRI to stage the extent of carcinoma of the breast, MRI has demonstrated significantly greater accuracy than mammography in defining tumor size when compared to pathology [140-143].

7.10.1 MRI Procedure

Each subject will be imaged in a whole body 1.0 Tesla or higher field strength MRI scanner using a dedicated breast imaging radiofrequency coil. The subject will lie prone on the table with both breasts hanging freely in the coil. The following pulse sequences will be performed in the transaxial orientation with a 32-40 cm field-of-view for bilateral coverage:

1. 2D or 3D spin echo or gradient echo localization sequence; 32-40 cm field of view (FOV), 5 cm slice thickness, number of locations to cover both breasts in I/S direction.

- 2D T2-weighted fast spin echo sequence; TR/TE = 5500 ms/85 ms, 24 slices, 3-4 mm slice thickness to cover both breasts in I/S direction, echo train length 8, 32-40 cm field of view (FOV), 512x256 matrix, Frequency A/P.
- 3. 3D fast gradient echo sequence without fat-saturation; TR/TE = 20 ms/minimum TE with Fat/Water in phase, 30 degree flip angle, FOV 32-40 cm, 60 slices, 1-2 mm slice thickness to cover entire breast in I/S direction, 512-256 matrix, frequency A/P.
- 4. 3D fast gradient echo sequence with fat-saturation; Repeat #3 with chemical saturation fatsuppression.

No contrast agent will be administered for this examination. Additional pulse sequences including diffusion-weighted and 3D steady state free procession sequences may be acquired depending on availability of these techniques on the MRI systems at the participating sites. The total exam time, including patient positioning will be less than 1 hour. Subjects are given the opportunity to lie in the magnet before scanning begins. Those subjects experiencing claustrophobia are counseled by a technologist or physician and will not be pressured to finish the exam. Earplugs are provided to each subject to reduce noise levels.

All MRI exams will be performed during the luteal phase of the menstrual cycle. Although diagnostic breast MRI is usually scheduled in the follicular phase of the menstrual cycle because it is easier to detect tumors, we will be using MRI to measure physiological characteristics of the breast, not to detect tumors or other abnormalities. Because non-contrast MRI scans to be used are not diagnostic, we do not anticipate detecting abnormalities. However, if abnormality is detected, the participant will be informed and the results will be sent in writing by the clinical center PI to the physician identified by the participant on the consent form.

7.10.2 Reproducibility of measurement of breast tissue total volume

In order to quantify the variability in breast volume measurement due to patient re-positioning, two normal volunteers, one with low and one with high mammographic breast density, were each scanned twice on the same day. Two different users delineated breast tissue regions as described above and the overall volume of fibroglandular tissue was calculated on the whole MR data set. The intra-user variability with patient repositioning was 2% for the dense breast and 8% for the fatty breast. The inter-user variability for the dense breast was 7% and for the fatty breast was 18.3%. The subjects in the DISC study will each receive only 1 MRI exam and therefore variability due to repositioning will not be a factor. Because of the young age of the study population, we anticipate that the majority of subjects will have dense breast tissue, the category in which the best reproducibility was measured. The same investigator will analyze all breast MRI studies.

7.10.3 Image Transfer

Data will be archived with patient identifying information replaced by study ID number. Image data will be sent by optical disk to University of California at San Francisco (UCSF) for breast density measurements.

7.10.4 Image Analysis

Image data will be processed at UCSF using customized image processing software to identify the chest wall/breast tissue boundary and skin surface, and to separate breast fibroglandular and fatty tissue. Total volumes of fibroglandular and fatty tissue will be computed separately for each breast. In problematic cases such as those with incomplete or failed fat-saturation, manual delineation will be used.

7.10.5 Quality Assurance Program

Prior to the start of subject enrollment, a training session for all site MRI technologists will be conducted at UCSF. Hands-on instruction will be provided to address patient positioning, breast positioning in coil, scan prescription, and data acquisition. In particular, technologists will be trained to recognize and correct failures due to incomplete fat-suppression, motion artifact, and inadequate

breast coverage. Each site will be provided with 2 breast tissue mimicking phantoms consisting of doped-water and oil compartments that will be used to periodically test bilateral breast MR imaging sequences at each site. In addition, before any participant exams, breast MRI data from 5 volunteers will be acquired from each site and sent to UCSF for review. Image quality will be evaluated and acceptability will be required for site certification.

7.11 Bone Densitometry

We will measure bone density using dual x-ray absorptiometry (DEXA). The entire DEXA examination is very low dose radiation and typically less than the daily effective dose from natural sources (cosmic radiation, environmental isotopes in our bodies and surroundings). When compared to other radiological procedures, this protocol is approximately 10 times less radiation than a chest x-ray and 10 times less radiation than received when flying round trip coast-to-coast.

7.11.1 Scan Protocol

The participant will be asked to disrobe and wear a hospital gown. (Buttons, heavy fabrics, bra clasp, etc., can all cause inaccurate results.) They will then lie down on the table of the DEXA device. This is typically a simple padded tabletop. The x-ray arm will make several passes over the patient for each scan mode. The following scans will be acquired:

- 1. Lumbar Spine: A/P or P/A view, default scan speed, L1 L4.
- 2. Proximal Femur: A/P or P/A view, default scan speed.
- 3. Whole body: default scan speed

The scan combination of dedicated proximal femur, lumbar spine (L1-L4), and whole body DEXA scans is important for this study for several reasons. Dedicated scans of the lumbar spine (L1-L4) and of the proximal femur are the most widely used combination for diagnosing osteoporosis and assessing fracturing risk since fractures at these sites (1) are best predicted by site-specific scans, and (2) these fractures have the highest morbidity. Bone density measures at these two sites will allow for direct comparison of these study results to most of the osteoporosis literature. The spine contains a high percentage of trabecular, or spongy, high turnover bone (66%) while the proximal femur contains more of a mix of trabecular and cortical (compact) bone. The whole body is comprised of 80% cortical bone. It is a measure of systemic bone health and responds slower to changes in bone turnover. Thus, it may contain more "memory" of the intervention than the localized spine and femur sites. The entire examination should take less than 30 minutes. Any of the currently manufactured DEXA devices from Hologic, Inc., or GE/Lunar are appropriate.

7.11.2 Reproducibility of Bone Density Measurements

DEXA provides precise composition analysis with a low radiation exposure (< 0.1 μ Gy). The precision error (1 SD) for total body bone mineral density is less than 0.01 g/cm² and the coefficient of variation for this SD is 1.8% [140]. The same investigator will analyze all DEXA scans.

7.11.3 Image Data Transfer

Data will be archived with patient identifying information replaced by study ID number. Image data will be sent by super disk to UCSF for bone density measurements.

7.11.4 Image Analysis

Image data will be processed at UCSF using customized image processing software. Bone mineral content (BMC) and bone area (AREA) will be measured and bone mineral density (BMD) will be calculated. BMC is the bone mass in grams of the region being measured and AREA, in square centimeters, is the area projected by the bone in a 2-dimensional x-ray image. BMD is the value most reported as DEXA bone density. It is found by dividing the BMC/AREA and is in units of grams per square centimeters, or g/cm². Bone density as measured by DEXA techniques is an areal density, not a true physical density (mass per unit volume). This is because the DEXA measure is derived from 2-

dimensional x-ray projections. Thus, DEXA bone density is affected by bone size as well as physical density, and areal BMD will always be confounded by bone size (e.g. participant height) unless corrected. There are several techniques to accomplish this. Carter [141] derived "bone mineral apparent density" or BMAD that takes into account that the spine vertebral body is close to cylindrical in shape and this information can be used to estimate the missing dimension. It was shown that BMAD = BMC/(Bone projected area)^{1.5}. The UCSF investigators have also derived a whole body apparent density that effectively removes bone size from whole body BMD[142]. We will derive these apparent density variables in our analysis to reduce the data scatter caused by participant differences. Any abnormalities will be reported to the participant's physician.

In addition to bone density, the whole body scan provides body composition. DEXA is the most precise method to estimate whole body percent fat, and the CV for repeated scans is ~1% [143]. This is part of the whole body protocol and requires no additional radiation or time. Because breast density and bone density are strongly correlated to body composition, the %fat will be used in multivariate analyses of these two outcome variables.

It is not anticipated that abnormalities will be detected by DEXA. However, if abnormality is detected, the participant will be informed and the results will be sent in writing by the clinical center PI to the physician identified by the participant on the consent form.

7.11.5 Quality Assurance Program

Since the study needs to be sensitive to even small changes bone density, a comprehensive quality assurance program has been included. DEXA devices can have calibration drifts or major service issues over the course of the study. However, it is possible to correct for these calibration drifts posthoc if appropriate phantoms are scanned as part of the protocol. The phantoms of choice for this study are the device-specific spine phantoms (come with each device and different for each manufacturer) and the Hologic Whole Body phantom. These phantoms accurately predict the in vivo calibration of the device such that changes in the phantom measures are used to directly correct participant data collected during that interval. The spine phantom is typically scanned once a day as standard practices at most clinical DEXA sites. The whole body phantom is critical since previous work by the UCSF investigators has shown that the typical spine quality control program does not predict the whole body calibration. The whole body phantom would be scanned 3 times a week. The UCSF investigators will use Cumulative Sums (CUSUM) statistics to determine when a change in the calibration has occurred [144].

DEXA participant scans will be acquired at each of the 6 clinical sites. To pool scan results from different DEXA devices, static calibration differences must also be corrected. Ideally, this is done by scanning the same individuals on all devices. However, this is impractical. We will circulate a single set of calibration phantoms to all sites. This set of phantoms is more complete than the daily phantoms and made available by the UCSF investigators. Machines of the same make and model will be readily cross calibrated using this phantom data. Devices from different manufacturers will be calibrated with in vivo calibration equations from the literature. The calibration and monitoring activities will be coordinated by one of our investigators from UCSF ([name]) who is an expert in this area. The DEXA cross calibration protocol will take about 1 hour, and be done once during the course of the study.

To insure data accuracy and conformity to the protocol, the following training and procedures will be used. One of the UCSF investigators will travel to each site and train local DEXA personnel on the protocol including any special patient positioning, data transfer issues, and phantom scanning procedures. Each site will then recruit five volunteers who will be scanned according to the study protocol. The scans will be sent to UCSF for evaluation. The clinical center will not recruit study participants until their test data meets study standards. After site certification, participant scans will be sent to UCSF for central analysis to ensure there are no clinic specific inaccuracies due to placing regions of interest slightly differently. Participant scans that are found to be inaccurate due to artifacts, motion, or poor positioning will be rejected from the study data and coded for the type of problem found. The UCSF investigators find approximately 5% of scans received from trained clinical sites have some type of quality issue.

7.12 Training and Certification

A centralized data collection training session will be held during the first year of the grant to train and certify individuals responsible for the different types of data collection except DEXA and breast MRI. [name] will perform DEXA training locally at each site as described above. Breast MRI training will be performed at the Univ. of California at San Francisco to allow adequate hands on time on the magnet. A technician from each center will be sent to San Francisco for this training. Each Clinical Center will have at least one person centrally trained and certified to collect each type of data who will train others at their center locally. Requirements for certification are:

- Height, Weight Repeat measurements within acceptable limits
- Diet Assessment NCC Training and Certification
- Other Questionnaires Receive passing grade on exam about procedures
- Blood Collection
 Receive passing grade on exam about procedures
- Breast MRI
 Completion of 5 acceptable breast MRI's on volunteers
- DEXA Completion of 5 acceptable DEXA measurements on volunteers

8.0 STUDY PARAMETERS

- Serum hormone levels
- Breast density
- Bone mineral density

9.0 PHARMACOKINETIC STUDIES

Not applicable.

10.0 OFF-STUDY CRITERIA

Not applicable.

11.0 DRUG FORMULATION AND PROCUREMENT INFORMATION

Not applicable.

12.0 STATISTICAL CONSIDERATIONS

12.1 Data Management

All data will be processed at Maryland Medical Research Institute (MMRI), the original Data Coordinating Center (DCC) for the DISC study. MMRI currently uses a multi-access data entry system based on the Teleform® data entry software. The Teleform® software allows a clinical center to send data forms to the DCC either through a fax machine, through the mail (to be scanned at the DCC), or through a Web-based data entry system. If the forms are sent through a fax machine or through the mail for scanning, the data are read from the form using OCR/ICR software and verified. A preliminary edit is performed prior to insertion into a transaction database. A comprehensive edit of the data in the transaction database is performed and sent via e-mail to the clinical center prior to acceptance of the form into the main study database. MMRI is currently using MS Access as the main database system for studies the size of the DISC Follow-up Study with edits and other procedures written in Visual Basic. The DISC database will be housed on the main MMRI server running Windows 2000.

The preliminary edit compares the study participant ID number (using the same number as in the main DISC study) and namecode (the same as used in the main DISC study) to the main study database, which will have the original information available. If the identifying information is verified as

correct, the other data are scanned to verify that the data are within preset ranges and are of the correct type. The comprehensive edit will look for consistency in the responses on the form and for consistency across forms (and against the previous DISC data). Data entry will have quality control checks built into the system. Each month 10% of forms will be verified manually against the main database. A test set of forms with multiple errors will be run through the data edit system routinely to verify that errors are caught and correct items are not. Timeliness of responding to edit queries will be tracked, as will the time between completion of the visit for a particular woman and when her forms are submitted.

A back-up of the databases and data management programs is performed every night with a weekly archive sent off-site to an environmentally controlled and protected storage facility. All user computers are fully backed up every week and, for the main statisticians on a study, every night. Access to the main study database is through multilevel password protection and enforcement of user privileges on the database. The main MMRI network is not accessible from the outside or from the Web except through passwords and a firewall. Access to any particular PC on the MMRI network can only be obtained through the granting of specific privileges to a particular individual.

12.2 Data Analysis

All analyses will be performed using analysis files created by adding follow-up data to the main DISC database with verification by manual checking. SAS (SAS Inst., Cary, NC) will be the primary software used for analysis supplemented with S-Plus (Insightful Corp., Seattle, WA) and Stata (Stata Corp., College Station, TX).

Because DISC was a clinical trial, analysis of the specific aims will be performed by randomized treatment assignment. Mean serum progesterone will be compared between the intervention and usual care groups without regard to compliance with the intervention, attendance at intervention sessions, or attendance at earlier DISC clinic visits. Because hormonal contraceptives contain progesterone, only women not using hormonal contraceptives will be included in analysis of treatment group differences in serum progesterone levels. The distribution of serum progesterone values will be examined to determine whether transformation is appropriate prior to analysis. In previous DISC analyses, we In transformed hormone concentrations to improve normality and decrease dependence of the variance on concentration. We anticipate that In transformation of progesterone data collected at the proposed follow-up visit will also be appropriate, but a final decision will be made after examining the data. The analytical approach will depend on the distributions of age, race, and menstrual cycle day when blood was collected at the clinic visit in the two treatment groups. These characteristics are potential confounders that would not be affected by the intervention. If the treatment groups are balanced on these characteristics, means can be estimated directly and statistical significance of the treatment group differences can be tested using a Student's t-test. If the participants in the treatment groups are not balanced on these characteristics and there is evidence for confounding, we will estimate adjusted means and test for statistical significance using linear models. We used analysis of covariance to compare adjusted treatment group means in previous DISC hormone analyses.

The effect of missing progesterone data on observed treatment group differences will be evaluated using the multiple imputation method of Rubin [89], in which multiple datasets are constructed, analyzed, and results combined so that the underlying variability of the outcome is preserved.

In secondary analysis of the primary aim, we will determine whether treatment group differences in progesterone are related to differences in several individual characteristics including age at menarche, BMI, and % body fat by including appropriate covariates in linear models. We will investigate if there is a particular component of the diet intervention (energy, total or saturated fat, fiber) responsible for observed differences in progesterone levels. BMI and diet at time of the follow-up visit or earlier, during puberty, could be responsible for observed treatment group differences in progesterone at the follow-up visits. To evaluate if puberty is a critical time for exposure, we will estimate the mean level of exposure at earlier DISC visits and use linear models to evaluate whether

average pubertal exposure can explain treatment group differences in progesterone levels at the follow-up visit. Furthermore, we will evaluate potential confounding and effect modification of treatment group differences in progesterone levels at follow-up visits by changes in characteristics such as diet, anthropometry, and physical activity between the last DISC visit and the follow-up visit and by intervening events such as pregnancy, lactation, and use of hormonal contraceptives, by including terms for main effects in models to evaluate confounding and by including cross-product terms in models that include main effects to evaluate effect modification.

Analysis of secondary aims will be performed using the same approach as described for the primary specific aim except breast MRI analysis will use statistical techniques for paired organs as described below. Similar to progesterone, women using hormonal contraceptives will not be included in analysis of serum estradiol. We will, however, perform breast MRI and bone densitometry on these women. In analysis of treatment group differences in breast density and bone density, we will evaluate confounding by past and present hormonal contraceptive use. We also will test for interaction of hormonal contraceptive use with treatment group effects by including cross-products terms in models. Analyses will be stratified by hormonal contraceptive use if cross-product terms are significant.

We will use the generalized estimating equations (GEE) approach to analyze the breast density data. GEE will be used to adjust for the inherent correlation between the density measures of the two breasts within the same woman. This modeling can be done as either a nested model with breast nested within women or as an explicit factor in the model with appropriate interaction terms. Although other data reduction techniques could be used (such as averaging the breast density measures for both breasts so that we would use the average breast density for a women in the analysis), the GEE approach would preserve the information about the density for each breast so that we can investigate variation in density between the two breasts.

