3.2 Primary Specific Aim

1. Determine the long-term effect of the DISC intervention on serum progesterone levels in early adulthood.

Hypothesis: Luteal phase serum levels of progesterone in the DISC intervention group are significantly lower than in the usual care (control) group at 25-29 years of age.

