5.2 Scheduling Clinic Visits

All clinic visits will take place during the luteal phase of participants' menstrual cycles. Although follicular phase estradiol levels in the intervention group were significantly 28% lower than the usual care group at Year-5 visits, we did not observe any significant differences in estrogens or androgens in the follicular phase of the menstrual cycle at last visits. However, at their last DISC visits, the intervention group had significantly 53% lower serum progesterone levels during the luteal phase of their menstrual cycles compared to the usual care group. To maximize power to observe differences in progesterone and possibly estrogens at the proposed follow-up visit, all visits will be scheduled to take place during the luteal phase of the menstrual cycle.

Because time from ovulation to onset of next menses is more constant than time from previous menses to ovulation, we will time visits in relation to expected date of start of next menses. The participant in consultation with clinic staff will select a target date for the clinic visit based on when she usually gets her period. When the participant starts her last period expected before the target date, she will call the clinic. Clinic personnel will record the date the participant started her last period and then schedule the visit to occur 3-4 days (± 2 day window) before her anticipated start of next menses based on date of start of last period and usual cycle length. We also considered timing the clinic visit in relationship to ovulation by asking participants to use urine ovulation kits. However, participants would have to come to the clinic in about a week after ovulating, which would give them little time for planning to take time off from school or work and in some cases fly to the clinical center. Additionally, using this approach we would include only ovulatory cycles, which would remove a source of variation in the hormone data.

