7.5 Menses Dates

Participants will report date of last menses and record date of start of next menses after the clinic visit on a postcard and return it to the clinic. Because data on start of next menses will be important for interpreting serum hormone and breast MRI data, if a postcard is not received within 5 days of estimated start of next menses, clinic staff will call the participant to see if she started her period. If she has, the date will be recorded. If she has not, clinic staff will call her each week until she has her period.

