12.3.1 Primary Specific Aim

We used data from the DISC last visit on serum progesterone levels in 9 usual care group participants whose blood was collected 1-6 days before the start of their next menses. This time frame is the window during which follow-up visits will take place in the proposed study. Earlier DISC analyses were performed on In transformed hormone values. We also used In transformed values to improve normality of distribution for these power calculations. The mean transformed progesterone concentration adjusted for age and cycle day was 6.76 (sd = 0.52). Hormones will be measured only in participants not using hormonal contraceptives. CDC estimates that 40% of women 20-24 years old use hormonal contraceptives [146]. In our pilot study of DISC participants, 48% of women reported using hormonal contraceptives and 10% were pregnant. Ninety-three percent of participants in our pilot said they would be willing to come to a follow-up visit. We estimated detectable differences in progesterone concentrations at 80% (conservative) and 90% participation rates assuming 50-60% of participants are using hormonal contraceptives or pregnant and cannot be included in these analyses (Table 1). Depending on participation rate, hormone use, and pregnancy we will be able to detect

Table 1. Minimal Detectable Differences For Luteal Phase Progesterone and Estradiol at α =.05 (2-sided) and 80% Power

| Participation Rates | Hormonal Contraceptive Use or Pregnant | Number per Group | Detectable Difference Progesterone | | Detectable Difference Estradiol | |
|------------------------|--|---------------------|---------------------------------------|---|------------------------------------|---|
| | | | In | % | In | % |

| 80% | 50% | 60 | .266 | 23.3% | .164 | 15.1% |
|-----|-----|----|------|-------|------|-------|
| | 60% | 48 | .297 | 25.7% | .183 | 16.7% |
| 90% | 50% | 68 | .250 | 22.1% | .154 | 14.3% |
| | 60% | 54 | .280 | 24.4% | .173 | 15.9% |

22%-26% lower progesterone levels in the intervention group compared to usual care ((e $^{6.76}$ – e $^{6.76}$ - $^{2.266}$)/e $^{6.76}$). At last DISC visits the intervention group's mean progesterone level was 52.9% lower than the usual care group. We will have ample power to detect a difference that is less than half as large as this.

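### Table 1's detectable differences rest on an SD adjusted for cycle day and timed to the next menses, but visits are booked on predicted menses and the balanced-groups analysis is an unadjusted t-test

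*Protocol*

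**What the plan says.** - **Target.** The primary hypothesis (Section 3.2) is that "Luteal phase serum levels of progesterone in the DISC intervention group are significantly lower than in the usual care (control) group".
- **Visit timing.** Section 5.2 has clinic staff "schedule the visit to occur 3-4 days (± 2 day window) before her anticipated start of next menses based on date of start of last period", with her typical cycle length also used. That is 1-6 days before a predicted date (3 − 2 to 4 + 2). Ovulation kits were rejected, partly because "using this approach we would include only ovulatory cycles, which would remove a source of variation in the hormone data".
- **Actual date.** Section 7.5 collects the true start of next menses by postcard and repeated calls: "Because data on start of next menses will be important for interpreting serum hormone and breast MRI data".
- **Who is analysed.** Section 12.2: "only women not using hormonal contraceptives will be included in analysis of treatment group differences in serum progesterone levels". Section 12.3.1 adds pregnancy, "assuming 50-60% of participants are using hormonal contraceptives or pregnant and cannot be included in these analyses". No criterion uses the recorded menses date.
- **How it is analysed.** Under Section 12.2, balance on age, race and cycle day leads to directly estimated means and a Student's t-test. Linear models enter only if there is imbalance together with evidence of confounding.
- **Planning SD.** Section 12.3.1 uses ln progesterone in nine usual care girls bled 1-6 days before their next menses: mean 6.76, SD 0.52, adjusted for age and cycle day. It then states: "This time frame is the window during which follow-up visits will take place in the proposed study". Section 12.3.2 does the same for estradiol (SD 0.32).

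**The concern.** Table 1 and the planned analysis differ in two ways.

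1. **Adjustment.** The SD has the cycle-day variation taken out. The t-test leaves it in. Balance between groups removes confounding by cycle day, but it does not remove the within-group variance that cycle day adds.
2. **Window.** Samples 1-6 days before predicted menses are samples 1-6 days before actual menses only if every prediction is exact. Some draws will fall earlier, and some could fall on or after onset, where progesterone is low.

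Both raise the SD above 0.52. The second can also dilute a luteal difference. Randomisation makes balance the expected outcome, so the unadjusted branch is the likely one. At stake is the claim in Section 12.3.1 of ample power for a difference less than half the earlier 52.9%. Estradiol inherits the same problem.

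**Working it through.** **1. Reproduce Table 1.** Numbers per group are 301 × participation × (1 − excluded) / 2: 60.2, 48.2, 67.7 and 54.2, as stated, with no deduction for mistimed samples. The detectable difference is (1.96 + 0.8416) × SD × √(2/n). For n = 60: 2.8016 × 0.52 × √(2/60) = .266, and 1 − e^(−.266) = 23.4%. The other rows give .297, .250 and .280. The arithmetic is right, given an SD of 0.52 in every analysed woman.

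**2. Perfect timing, no adjustment.** The documents give no hormone profile, so one is assumed: 10 ng/ml seven or more days before menses, falling to 1.5 on the day before and 0.5 from onset, with residual SD 0.52 on the ln scale.
- Log-linear slope: ln(10/1.5)/6 = 0.316 per day.
- Days 1-6 equally likely: SD √(35/12) = 1.708 days.
- Spread due to day: 0.316 × 1.708 = 0.54.
- Unadjusted SD: √(0.52² + 0.54²) = 0.75.
- Power = Φ(.266/(0.75 × √(2/60)) − 1.96) = Φ(1.94 − 1.96) = 49%.

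A fall that is linear in ng/ml gives SD 0.79 and power 46%. A log-linear fall half as steep gives √(0.52² + 0.27²) = 0.59 and power of about 70%.

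**3. Add prediction error.** The error is assumed normal and rounded to whole days, with SD 2 or 3 days. Ranges cover the two shapes of fall. Power is at .266, starting from 60 per group.

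| Error SD | Truly 1-6 days before | On or after onset | SD, all visits | Power, all visits | SD, pre-menses only | n left | Power, pre-menses only |
|---|---|---|---|---|---|---|---|
| 0 | 100% | 0% | 0.75-0.79 | 46-49% | 0.75-0.79 | 60 | 46-49% |
| 2 | 74% | 13% | 1.04-1.08 | 27-29% | 0.78-0.80 | 52 | 40-41% |
| 3 | 61% | 19.5% | 1.16-1.20 | 23-24% | 0.80-0.84 | 48 | 35-38% |

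The all-visits column credits every sample with the full difference. If samples on or after onset carry none, .266 shrinks by their share and power is about 16-23%.

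**4. Check without a profile.** Let a share f of samples be lower by g ln units. Then SD = √(0.52² + f(1 − f)g²). With f = 5% and g = 1.5 to 3.0, the SD is 0.61-0.84 and power 66-41%. With f = 10% it is 0.69-1.04 and 56-29%.

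**5. The earlier difference.** −ln(1 − .529) = .753. At n = 60 power exceeds 99% with perfect timing. With all visits and error SD 2-3 days it is 93-98%, or 79-93% if samples from onset carry no effect. With pre-menses samples only it is about 99%.

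**6. Table 1 with an allowance.** With SD 0.52 and 10% fewer women, the detectable differences are .263-.313 (23.2%-26.9%). With 20% fewer they are .279-.332 (24.4%-28.3%). Estradiol, SD 0.32: 2.8016 × 0.32 × √(2/61.2) = .162 (15.0%) at best (68 × 0.9) and 2.8016 × 0.32 × √(2/38.4) = .205 (18.5%) at worst (48 × 0.8), against 14%-17% stated.

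**The case against.** - **The set may not be exhaustively defined.** A reader might infer that contraceptive non-use is the whole definition and that women already bleeding would be analysed as luteal. The documents do not support that. Section 12.3.1 also excludes pregnancy, and Sections 5.0, 5.2 and 7.10.1 require visits or scans in the luteal phase, so a visit after onset would depart from the plan. An exact day-count rule could also sit in an analysis plan that is not shown. This stands, and it is why the pre-menses column matters more than the all-visits column. It does not rescue the stated adjustment rule or the equation of the two windows.
- **Much of the loss is not mistiming.** This also stands. With zero prediction error, the assumed profile already takes power to 46-49%. The main gap is between an adjusted SD and an unadjusted test.
- **The SD might be raw.** Section 12.3.1 attaches the adjustment to the mean and gives the SD in brackets after it. If 0.52 were unadjusted, the perfect-timing loss would vanish. The mistiming loss in step 4 would remain.
- **Restriction selects after randomisation.** Section 2.1.3 supposes that the intervention may have reprogrammed the HPO axis, which could alter cycles, and Section 5.2 did not want ovulatory cycles alone. Section 12.2 does treat cycle day as unaffected by the intervention. Even so, this is a good reason not to let a restricted set replace the full one. A limit of 14 days to next menses would gain almost nothing: it removes under 1% of samples in the model above.
- **The sample is fixed.** No recruitment number changes. The analysis and the stated detectable differences still can.

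**Conclusion.** The point holds as a mismatch between Table 1 and the analysis in Section 12.2. The 22-26% detectable differences need cycle-day adjustment and accurate timing to actual menses. The plan makes the first conditional and does not secure the second.

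Under the assumed profile, power at .266 with 60 per group is about 46-49% unadjusted with perfect timing. With a prediction-error SD of 2-3 days it is about 35-41% without visits after onset and about 23-29% with them, against 80% stated. The profile, the error SD and the share of mistimed visits are all assumptions, and a shallower fall gives a smaller loss.

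A reader might infer that the trial is underpowered overall. The documents do not support that, because power for the earlier 52.9% difference remains much higher. The weakness lies in the claim about differences less than half that size.

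**What to change.** 1. In Section 12.2, make the primary progesterone and estradiol analysis a linear model that always includes age and actual days from blood draw to next menses, whether or not the groups are balanced. Categories of days would accommodate very early, late and post-onset draws.
2. Before unblinding, pre-specify an analysis limited to samples that the recorded menses date confirms as pre-menses. Report it beside the analysis of all eligible women (non-users, not pregnant). State that the restriction selects on a post-randomisation event and costs some women.
3. In Section 12.3, say that the follow-up window is set on predicted menses, and restate Table 1 with an allowance for mistimed samples: with SD 0.52 and 10-20% fewer women, about 23-28% for progesterone. The SD of 0.52 is then the planning value for the day-adjusted model; it is not shown by the calculation above, which took it as input.

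The cost is a few sentences and a revised table. The menses date is already collected, and no visit, assay or recruitment number changes.
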